10.2 Statistical Methods

Statistical analysis: The correlation of biopsy tissue histopathology with intraprostatic MRI findings will be estimated using binomial evaluation for True Positive, False Positive, True Negative, False Negative values to report Sensitivity, Specificity, and Positive as well as Negative Predictive value for parametric MRI findings relative to correlated histopathology. These data will be used for reporting the study results in regards to Specific aim 1, The infection rate and hospitalization rate within 30 days due to the procedure will be collected for expected acute events (AE's) and these data will be used for reporting the study results for specific aim 2 evaluation the transperineal use of Uronav to determine if the transperineal biopsy approach results in a reduced rate of infection or hospitalization compared to standard transrectal biopsies.

Any deviations from the previously described statistical plan will be described and justified in a protocol amendment.

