The use of MRI imaging has become increasingly more prevalent in the guidance of prostate biopsies both in the United States and internationally. Studies have confirmed that the use of MRI imaging to help direct the location of biopsies has increased both the frequency of diagnosing cancer, but even more importantly diagnosing clinically significant higher grade disease (5, 6). Several commercially available devices have come to market that aid in the ultrasound guidance of prostate cancer in patients that have had an MRI obtained prior to the biopsy (7). These devices may be designed for either transrectal or transperineal guided biopsy. Almost all of these manufactures have relied on the ability to use image fusion to align a real time transrectal ultrasound image of the prostate to the previously acquired MR image. By using segmentation tools to define high risk volumes likely to harbor cancer, these systems aid in the placement of a biopsy needle to the site of a suspected tumor foci. One such system, Uronav, developed by a subsidiary of Philips Medical, InVivo, has been FDA approved for routine use in transrectal guided biopsies of the prostate gland using an electromagnetic (EM) sensory system to help guide the biopsy needle tip to within 2 mm of the desired biopsy target defined by MRI. They have developed an additional version for transperineal biopsy as well and seek a validation trial to assess this platform.

Routinely all patients at University Hospitals schedule to receive prostate brachytherapy treatment undergo a 3T MR imaging of the pelvis and prostate to plan prostate brachytherapy. At the time of the brachytherapy procedure a transrectal ultrasound probe is used to image the prostate, and a commercially available computer planning system, Symphony (MIM Software, Beachwood,

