2.0 Study Objectives

Specific Aim 1: Evaluate final pathology post-operatively for histopathology confirmation of multiparametric MRI targets detected during treatment planning. This will be accomplished by using transperineal biopsies obtained prior to interstitial brachytherapy during the procedure, while under anesthetic just prior to the placement of the brachytherapy needles and sources.

Specific Aim 2: Evaluate the ability of the Uronav system in a transperineal setting to guide biopsy needle placement using the electromagnetic guidance system and transperineal ultrasound probe stabilization device and stepper.

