3.3 Secondary Study Endpoints

3.3.1 We will report the post-operative radiation dose coverage for the prostate, organs at risk, and targeted lesion for each case. The coverage for the brachytherapy implant will be reported for the V100, V150, and V200, i.e. volumes of the prostate receiving 100, 150, and 200% of the prescribed dose. The dose delivered to the targeted lesion or lesions will be reported as a V100, V150, V200 as well to evaluate the ability to target the dose escalation prospectively, though again is per routine and not as part of a therapeutic trial design at this time. Additionally, the D90, i.e. dose to 90 percent of the prostate volume will be reported. Doses to the bladder, rectum and urethra will also be calculated for evaluation in the study.

3.3.2 An additional secondary endpoint for the study will be to report the incidence of successful completion of the transperineal biopsy procedure using the Uronav system which is provided by Philips Medical as part of the support for this study. The Symphony biopsy system will be available in the operating room (OR) as a back-up to complete the biopsies if needed. It is, however, anticipated that the combined DynaCAD computer for processing the MR images and Uronav systems supplied for the study to integrate with our standard transperineal ultrasound system will be 100% successful in obtaining the required biopsies. We will also report on any unanticipated complications or infections. It is anticipated that the risk of infection should be substantially diminished by avoiding transrectal biopsies. However, the risk for prostate edema and urinary obstruction may be increased due to the additional transperineal needle placement as the biopsy will be followed by routine prostate brachytherapy. Patients may therefore be asked to maintain a Foley catheter overnight to allow edema to resolve, and avoid acute obstruction the following day. Assuming the Uronav system is capable of completing biopsies on all patients and no more than 1 patient acquires a post-operative infection this pilot study will be deemed a success, and further investigation may be warranted.

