4.0 Subject Selection and Withdrawal

4.1 General Characteristics of the Proposed Subject Population

The subject population will be screened from males with low to intermediate risk prostate cancer Gleason score $\leq 7(4+3)$ with PSA below 15 ng/mL who are consented for prostate low dose rate brachytherapy. They will qualify for the study if the planning MRI used for screening and brachytherapy source planning shows at least one region within the prostate that is reported as probable for malignancy by a Diagnostic Radiologist. Treatment planning will be performed per routine, and thus this trial is deemed non-therapeutic as it will not alter treatment. The patient's Urologist will consent them if desired for this study, and will perform the biopsies in the OR prior to proceeding with the prostate brachytherapy procedure as routinely performed with Radiation Oncology and the biopsy locations will be tracked with virtual fiducial markers using the Uronav system in addition to gold fiducial markers. The cost for the additional histopathology will be covered by the study along with required supplies.

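### Aim 2 asks whether Uronav can guide the needle transperineally, but Section 10.2 reports it with infection and hospitalization rates, and no endpoint records whether a targeted core reached its MRI target

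*Combined protocol and SAP*

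**What the plan says.** Section 2.0 states Aim 2 as: "Evaluate the ability of the Uronav system in a transperineal setting to guide biopsy needle placement using the electromagnetic guidance system", together with the probe stabilization device and stepper.

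Section 10.2 collects infection and hospitalization within 30 days due to the procedure, and says "these data will be used for reporting the study results for specific aim 2 evaluation the transperineal use of Uronav". The stated purpose is "to determine if the transperineal biopsy approach results in a reduced rate of infection or hospitalization compared to standard transrectal biopsies". Section 3.4 already makes infection or hospital admission within 30 days the primary safety endpoint.

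The device-performance endpoint is in Section 3.3.2: to "report the incidence of successful completion of the transperineal biopsy procedure using the Uronav system", with Symphony in the operating room as back-up. That section expects 100% success. It calls the pilot a success if Uronav completes the biopsies in all patients and no more than one patient has a post-operative infection.

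Location data are planned. Section 4.1 says that "the biopsy locations will be tracked with virtual fiducial markers using the Uronav system in addition to gold fiducial markers". Section 6.1 has target volumes defined in DynaCAD and transferred to Uronav, and a virtual fiducial placed at the biopsy site. Section 1.2 mentions needle-tip accuracy as background: the FDA-approved transrectal system uses electromagnetic sensing "to help guide the biopsy needle tip to within 2 mm of the desired biopsy target".

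**The concern.** The analysis assigned to Aim 2 answers a different question from the one the aim asks. Infection and hospitalization rates describe the safety of the transperineal route. They do not show whether the needle went where the system directed it. A team following 10.2 as written would report Aim 2 without any statement about guidance.

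This matters because Section 1.2 presents the study as a validation of the transperineal platform, and Section 4.1 gives the goal as feasibility of tracking histopathology location against MR imaging. Both depend on where the cores were taken.

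The primary endpoint is also touched. A negative targeted core may mean that the MRI finding was false or that the needle missed it, and 10.2 does not say how such cores are scored.

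**Working it through.** **The plan's own figure.** The only computed design figure is the 82% power in Section 10.1 (84 sites, 22% versus 11%, two-sided 0.05). It reproduces: Φ[((0.22 − 0.11)√84 − 1.96√(0.11 × 0.89)) / √(0.22 × 0.78)] = 83.0%, within about a point. It concerns the detection rate and has no bearing on Aim 2.

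**Where guidance could be measured.** The relevant sections, taken in turn:

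| Section | What it measures | Does it show that the needle reached the target? |
|---|---|---|
| 3.2 | Agreement of histology with MRI | No |
| 3.3.2 | Completion with Uronav; infection count | Not as worded; *successful* is not defined by a hit or a distance |
| 3.4 | Infection or admission, 30 days | No |
| 9.2 | Obstruction, infection, MRI correlation | No |
| 9.3 | Histology for each targeted lesion | Only indirectly; a negative core is ambiguous |
| 10.2, Aim 2 | Infection and hospitalization, 30 days | No |

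The fiducials in 4.1 and 6.1 record location, but no section derives a distance or a hit criterion from them.

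**The success rule.** Take completion as 100%, as 3.3.2 anticipates. With infection probability q per man (assumed; the documents give none), P(success) = P(at most 1 infection in 6) = (1 − q)^6 + 6q(1 − q)^5:

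| q (assumed) | P(success) |
|---|---|
| 2% | 0.994 |
| 5% | 0.967 |
| 10% | 0.886 |
| 20% | 0.655 |

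The rate at which targets are missed does not enter. For illustration, assume one target per man and independent misses with probability m. The chance of at least one missed target in six is 1 − (1 − m)^6, which is 0.47 at m = 10%, 0.74 at 20% and 0.88 at 30%. At q = 5%, P(success) stays at 0.967 throughout.

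**The comparison that 10.2 proposes.** There are six men, no control arm, no transrectal reference rate and no test.
- 0/6 infections, the best possible result: exact 95% upper limit = 1 − 0.025^(1/6) = 1 − 0.541 = 46%. With a one-sided 95% limit, 1 − 0.05^(1/6) = 39%.
- 1/6, which still passes the success rule: exact 95% interval 0.4% to 64%.

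Even zero events would therefore show a reduction only against a transrectal rate above about 46% (39% one-sided).

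**Precision of completion.** For 6/6 completed, the exact 95% lower limit is 0.025^(1/6) = 54%. This limit describes completion and says nothing about targeting.

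**The case against.** **Aim 2 is not wholly unmeasured.** Section 3.3.2 already counts completion with Uronav, names Symphony as back-up only, and makes Uronav completion part of the success rule. The required biopsies include the targeted ones (3.2). This stands. The gap is that 10.2 does not link completion to Aim 2, and that completion is not defined by reaching the target. A reader might infer that the protocol declares a missed lesion a success. It does not say so; that follows only from the rule's wording with *successful* left undefined.

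**A miss need not become an MRI false positive.** A reader might infer that every needle miss lowers the Aim 1 positive predictive value by a calculable amount. The documents do not support that. Section 6.1 ties each core to its recorded location, so a core recorded outside the lesion could be compared with MRI at that location. Section 9.3 reports by targeted lesion, which points the other way, and 10.2 gives no scoring rule. No miss rate or expected predictive value is stated, and a core that misses its target may still contain cancer. What stands is that the scoring is open.

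**A distance taken inside Uronav cannot fully validate Uronav.** If the fusion is misaligned, a fiducial can lie inside the contour while the needle missed the lesion, or the reverse. This stands and limits what the measure can claim. The gold markers in 4.1 might offer an outside check, but the plan does not say how they would be used.

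**This is a six-man feasibility pilot, and 9.2 expects no statistical analysis of effectiveness.** That is a good reason not to set a pass mark in millimetres. It does not prevent descriptive reporting, and it weakens the case for the comparative claim in 10.2.

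**Conclusion.** The point holds as a wrong assignment of analysis to aim. Section 2.0 asks about guidance, while 10.2 reports safety rates that already belong to 3.4 and attaches a comparison that six men cannot support (upper limit 46% at 0/6). No section turns the planned location data into a targeting measure, and as worded the success rule in 3.3.2 has no targeting term.

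The textual mismatch needs no assumption. The success probabilities rest on assumed infection rates and on completion at 100%; the miss illustration also assumes one target per man and independence. No size can be put on any effect on the Aim 1 predictive value. The matter should be corrected before analysis; it does not call the trial's conduct into question.

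**What to change.** In Section 10.2, report Aim 2 by:

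1. The 3.3.2 completion endpoint, counted per patient and per targeted lesion, with completion defined as done with Uronav without the Symphony back-up.
2. Descriptively, for targeted cores only: whether the recorded virtual fiducial lies inside the MRI target contour, and its distance in mm from that contour, summarised per man.

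Report infection and hospitalization under the 3.4 safety endpoint, and delete the statement that the study will determine a reduced rate compared with transrectal biopsy.

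As a sensitivity display, show the Aim 1 positive predictive value with and without targeted cores recorded outside the target, and state in 10.2 how such cores are scored.

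Label the distance as placement relative to the fused image. It does not capture fusion or deformation error, which can act in either direction, so it should not be called a lower bound. The 2 mm in 1.2 describes the transrectal system and may be cited only as a descriptive reference.

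The cost is a small export and analysis task, with no added subjects or biopsies. It covers only the targeted cores; the 84 sites also include standard sextant cores, and the plan does not give the split. That coordinates can be exported easily is an assumption to confirm with the device supplier.

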1.4 Clinical Data to Date

The NCI went on to complete a human trial using the electromagnetic guidance system to compare MRI directed biopsies versus routine sextant biopsies in a series of 101 patients with a known diagnosis of prostate cancer. The data confirmed the transrectal ultrasound guided biopsy of the fused ultrasound and MR images yielded a higher rate of positive biopsies and also increased the yield for positive biopsies of high Gleason grade disease than routine ultrasound imaging directed biopsy alone (6). Limitations for the transrectal system include difficulty in placement of biopsy needles into regions seen in the anterior gland or transitional zone, as well as the increasingly prevalent risk of post procedural infections or rectal bleeding presumably related to the transrectal needle placement (9, 10).

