3.4 Primary Safety Endpoints

The primary safety endpoint for the study will be the rate of infection or hospital admission within 30 days that are felt to be directly related to the procedure.

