4.2 Anticipated Number of Research Subjects

The pilot study is designed to include only 6 subjects for testing of feasibility to obtain transperineal tissues and report correlation to MRI image findings.

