9.2 Effectiveness Assessments

Effectiveness will be analyzed by the rate of urinary obstruction beyond 7 days or infection directly related to the procedure, in addition to the analysis for the correlation of the biopsy samples with preoperative MR imaging. Statistical analysis of effectiveness is not anticipated due to the limited number of subjects in this exploratory initial analysis.

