10.0 Statistical Plan

10.1 Sample Size Determination

Sample size justification: This is a hypothesis-generating pilot study with enrollment of 6 patients. Each patient is expected to have 12 to 15 tissue samples using standard sextant biopsies in addition to targeted biopsies of intraprostatic MRI findings. Assuming 14 specimens are sent for histopathology analysis in 6 subjects we will use the 84 biopsy sites. Based on the report in the literature [6], we expect the cancer lesion detection rate of 22% using multiparametric MRI/US fusion vs. 11% under current standard care. Ignoring the potential correlation of multiple lesions from the same patient, 6 patients (84 lesions) will have 82% power to detect in 11% improvement of detection rate using 2-sided one-sample chi-square test with a significance level of 0.05.

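### Section 10.2 sets out to determine whether transperineal biopsy lowers infection or hospitalization versus transrectal biopsy, which one cohort of 6 men with no comparator cannot do (minor)

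*Combined protocol and SAP*

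**What the plan says.** Section 10.2 (Statistical Methods) states that procedure-related infection and hospitalization rates within 30 days will be collected and used to report on Specific Aim 2, "to determine if the transperineal biopsy approach results in a reduced rate of infection or hospitalization compared to standard transrectal biopsies". The same section says that deviations from the statistical plan will be justified in a protocol amendment.

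Other sections bear on this:

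- **3.4** defines the primary safety endpoint as "the rate of infection or hospital admission within 30 days that are felt to be directly related to the procedure". It mentions no comparator.
- **4.2** says the study is "designed to include only 6 subjects for testing of feasibility to obtain transperineal tissues", and **10.1** says "This is a hypothesis-generating pilot study with enrollment of 6 patients".
- **6.1** has every subject biopsied transperineally, before routine brachytherapy under general anesthesia.
- **9.2** counts procedure-related infection under effectiveness and says "Statistical analysis of effectiveness is not anticipated due to the limited number of subjects in this exploratory initial analysis".
- **1.4** and **3.3.2** describe the transrectal risk in words only: "increasingly prevalent risk of post procedural infections or rectal bleeding presumably related to the transrectal needle placement", and the expectation that the "risk of infection should be substantially diminished by avoiding transrectal biopsies".
- **3.3.2** sets the success rule, conditional on Uronav completing every subject's biopsies: "no more than 1 patient acquires a post-operative infection this pilot study will be deemed a success, and further investigation may be warranted".

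**The concern.** To determine that a rate is reduced, a plan needs something to compare it with, a rule for deciding, and enough subjects for the result to be informative. Section 10.2 names the comparison and supplies none of these. The sentence stands in the statistical methods, so an author following it would report the safety data as an answer to the comparative question. Section 17.0 anticipates an abstract or manuscript.

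What is at stake is an unsupported safety claim in the report. A result of 0 or 1 event in 6 men could be presented as evidence that the transperineal route is safer, although such a result is quite likely even if the route makes no difference.

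**Working it through.** **The plan's own figure.** No power or precision figure is given for infection or hospitalization. The only power statement (10.1) concerns lesion detection, 22% versus 11% over 84 sites treated as independent, with a two-sided 0.05 test and 82% power. It reproduces closely by the normal approximation:

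Φ[(0.11·√84 − 1.96·√(0.11·0.89)) / √(0.22·0.78)] = Φ[(1.008 − 0.613) / 0.414] = Φ(0.953) = 83.0%.

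It has no bearing on the safety comparison, where the unit is the man and n is 6.

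**Inputs.**
- n = 6, one cohort (4.2, 10.1).
- Transrectal arm: none (6.1).
- Transrectal rate: not given (1.4 and 3.3.2 are qualitative). I assume 2%, 5% and 10% to show a range.

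**Step 1: precision of the possible results.** Exact (Clopper-Pearson) 95% intervals:
- 0/6: upper limit = 1 − 0.025^(1/6) = 0.459, so 0 to 45.9%.
- 1/6: lower limit = Beta(0.025; 1, 6) = 0.004 and upper limit = Beta(0.975; 2, 5) = 0.641, so 0.4 to 64.1%.

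Even with no events, the interval would exclude only a transrectal rate above 45.9%.

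**Step 2: how often a clean result arises with no reduction.** If the true rate equals the transrectal rate p, then P(0 of 6) = (1 − p)^6:

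| Assumed p | Calculation | P(0/6) |
|---|---|---|
| 2% | 0.98^6 | 89% |
| 5% | 0.95^6 | 74% |
| 10% | 0.90^6 | 53% |

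At each of these assumed rates, zero events is more likely than not when the route changes nothing.

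**Step 3: scale.** For zero events to exclude a fixed rate p at the same level, n must satisfy (1 − p)^n ≤ 0.025, that is n ≥ ln(0.025)/ln(1 − p). This gives 36, 72 and 183 men for p = 10%, 5% and 2%.

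**Step 4: attribution.** The biopsies are followed in the same session by the implant, which typically uses 20 to 35 transperineal needles (1.2, 6.1). An infection or admission within 30 days could come from either. Even with a stated transrectal rate, the observed events would not isolate the biopsy route.

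**Step 5: consistency with other sections.** A comparative determination goes beyond the hypothesis-generating purpose in 10.1 and the feasibility purpose in 4.2. It also sits badly with 9.2, which for infection expects no statistical analysis of effectiveness because the numbers are small.

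**The case against.** The strongest reply is that this is one loosely worded purpose clause at the end of a sentence whose operative content is collecting and reporting data. The pilot, feasibility and exploratory labels in 4.2, 9.2 and 10.1 already limit interpretation, and success under 3.3.2 leads only to possible further investigation. Much of this stands, and it is why the point is minor. The labels do not make the clause correct, however; they are at odds with it.

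A reader might infer more than the documents support in three ways:

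- **That 10.2 and 9.2 plan contradictory analyses.** They do not. Section 10.2 names no test, and 9.2 also looks at the rate of infection. The tension is confined to the claim to determine a reduction, and it concerns infection only, since 9.2 does not mention hospitalization.
- **That the success rule in 3.3.2 is meant as the comparison with transrectal biopsy.** No section presents it that way. Its limit on infections refers to no transrectal rate.
- **That Specific Aim 2 has no relevant analysis.** Aim 2 (2.0) concerns needle guidance, and safety is all that 10.2 links to it. But 3.3.2 already plans to report successful completion with Uronav; 10.2 simply does not refer to it.

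**Conclusion.** The clause is wrong as written: the design cannot determine whether infection or hospitalization is reduced relative to transrectal biopsy. The absence of a comparator, a reference rate and a decision rule is enough to establish this, and the intervals of 0 to 45.9% (0/6) and 0.4 to 64.1% (1/6) show how little 6 men can say. Those intervals rest only on n = 6. The probabilities of 89%, 74% and 53% rest on assumed rates, because the documents give none.

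Severity is minor. It would go too far to read this as undermining the trial's conduct or decisions: the primary endpoint, the 3.4 safety endpoint, the 3.3.2 success rule and the stopping rule (10.3, 11.8) do not use the comparison. The effect is limited to what may be concluded and reported.

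**What to change.** In 10.2, end the sentence before the clause that states the comparison with transrectal biopsy, delete that clause, and add:

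> The 30-day procedure-related infection and hospitalization rates will be reported descriptively with exact 95% CIs; no inference of a reduction versus transrectal biopsy will be drawn.

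Optionally, cross-reference the Uronav completion endpoint in 3.3.2 as the feasibility report for Specific Aim 2, leaving its definition as it is.

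The cost is a short text edit. Both rates are already collected, so no new data are needed, and no endpoint, success rule or stopping rule changes. The trial gives up a comparative statement that it could not have supported.
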